10.4 Confirmatory Measurement/Duration of Response

10.4.1 Duration of overall response

The duration of overall response is measured from the time measurement criteria are met for CR or PR (whichever is first recorded) until the first date that recurrent or progressive disease is objectively documented (taking as reference for progressive disease the smallest measurements recorded since the treatment started).

The duration of overall CR is measured from the time measurement criteria are first met for CR until the first date that recurrent disease is objectively documented.

10.4.2 Duration of Stable Disease

Stable disease is measured from the start of the treatment until the criteria for progression are met, taking as reference the smallest measurements recorded since the treatment started.

11.0 Serious Adverse Event Reporting (SAE)

An adverse event or suspected adverse reaction is considered “serious” if, in the view of either the investigator or the sponsor, it results in any of the following outcomes:

- Death
- A life-threatening adverse drug experience – any adverse experience that places the patient, in the view of the initial reporter, at immediate risk of death from the adverse experience as it occurred. It does not include an adverse experience that, had it occurred in a more severe form, might have caused death.
- Inpatient hospitalization or prolongation of existing hospitalization, unless hospitalization is for:

- routine treatment or monitoring of the studied indication, not associated with any deterioration in condition (specify what this includes)
 - elective or pre-planned treatment for a pre-existing condition that is unrelated to the indication under study and has not worsened since the start of study drug
 - treatment on an emergency outpatient basis for an event not fulfilling any of the definitions of a SAE given above and not resulting in hospital admission
 - social reasons and respite care in the absence of any deterioration in the patient’s general condition
- A persistent or significant incapacity or substantial disruption of the ability to conduct normal life functions.
 - A congenital anomaly/birth defect.
 - Important medical events that may not result in death, be life threatening, or require hospitalization may be considered a serious adverse drug experience when, based upon appropriate medical judgment, they may jeopardize the patient or subject and may require medical or surgical intervention to prevent one of the outcomes listed in this definition. Examples of such medical events include allergic bronchospasm requiring intensive treatment in an emergency room or at home, blood dyscrasias or convulsions that do not result in inpatient hospitalization, or the development of drug dependency or drug abuse (21 CFR 312.32).
 - Important medical events as defined above, may also be considered serious adverse events. Any important medical event can and should be reported as an SAE if deemed appropriate by the Principal Investigator. All events occurring during the conduct of a protocol and meeting the definition of a SAE must be reported to the IRB in accordance with the timeframes and procedures outlined in “The University of Texas M. D. Anderson Cancer Center Institutional Review Board (IRB) Policy for Investigators on Reporting Unanticipated Adverse Events for Drugs and Devices”. For this protocol adverse events will be captured according to the Recommended Adverse Event Recording Guideline for Phase II protocols (below).

Recommended Adverse Event Recording Guidelines					
Attribution	Grade 1	Grade 2	Grade 3	Grade 4	Grade 5
Unrelated	Phase I	Phase I	Phase I Phase II	Phase I Phase II Phase III	Phase I Phase II Phase III
Unlikely	Phase I	Phase I	Phase I Phase II	Phase I Phase II	Phase I Phase II

				Phase III	Phase III
Possible	Phase I	Phase I	Phase I	Phase I	Phase I
	Phase II	Phase II	Phase II	Phase II	Phase II
		Phase III	Phase III	Phase III	Phase III
Probable	Phase I	Phase I	Phase I	Phase I	Phase I
	Phase II	Phase II	Phase II	Phase II	Phase II
		Phase III	Phase III	Phase III	Phase III
Definitive	Phase I	Phase I	Phase I	Phase I	Phase I
	Phase II	Phase II	Phase II	Phase II	Phase II
		Phase III	Phase III	Phase III	Phase III

The Investigator or physician designee is responsible for verifying and providing source documentation for all adverse events and assigning the attribution for each event for all subjects enrolled on the trial

- **Serious adverse events will be captured from the time of the first protocol-specific intervention, until 30 days after the last study treatment/intervention, unless the participant withdraws consent. Serious adverse events must be followed until clinical recovery is complete and laboratory tests have returned to baseline, progression of the event has stabilized, or there has been acceptable resolution of the event.**
- **Additionally, any serious adverse events that occur after the 30 day time period that are related to the study treatment must be reported in accordance with the IRB policy. This may include the development of a secondary malignancy.**

Reporting to FDA:

- SAE's will be reported per regulatory (local and federal) guidelines.

It is the responsibility of the PI and the research team to ensure that serious adverse events are reported according to the Code of Federal Regulations, Good Clinical Practices, the protocol guidelines, the supporter guidelines, and Institutional Review Board policy.

Investigator Communication with Supporting Companies:

Reporting to Novartis for patients taking Pazopanib

All events reported to the FDA by the investigator are to be filed utilizing the Form FDA 3500A (MedWatch Form).

To ensure patient safety, every SAE, regardless of suspected causality, occurring

- after the patient has provided informed consent and until at least 30 days after the patient has stopped study treatment/participation
- after protocol-specified procedures begin (e.g., placebo run-in, washout period, double-blind treatment, etc.) and 30 days after the patient has stopped study treatment
- after the start of any period in which the study protocol interferes with the standard medical treatment given to a patient (e.g., treatment withdrawal during washout period, change in treatment to a fixed dose of concomitant medication) and until 30 days after the patient has stopped study treatment

All Events must be reported to Novartis within 24 hours of learning of its occurrence

Information about all SAEs is collected and recorded on a Serious Adverse Event Report Form; all applicable sections of the form must be completed in order to provide a clinically thorough report. The investigator must assess and record the relationship of each SAE to each specific study treatment (if there is more than one study treatment), complete the SAE Report Form in English, and **send the completed, signed form by fax to ([contact]) within 24 hours to the oncology Novartis DS&E department with the provided FAX cover sheets.**

This includes serious, related, labeled (expected) and serious, related, unlabeled (unexpected) adverse experiences. All deaths during treatment or within 30 days following completion of active protocol therapy must be reported within 5 working days.

Any SAEs experienced after this 30 days period should only be reported to Novartis if the investigator suspects a causal relationship to the study drug. Recurrent episodes, complications, or progression of the initial SAE must be reported as follow-up to the original episode within 24 hours of the investigator receiving the follow-up information. A SAE occurring at a different time interval or otherwise considered completely unrelated to a previously reported one should be reported separately as a new event. The end date of the first event must be provided.

The original copy of the SAE Report and the fax confirmation sheet must be kept within the Trial Master File at the study site.

Follow-up information is sent to the same fax number as the original SAE Report Form was sent, using a new fax cover sheet, stating that this is a follow-up to the previously reported SAE, and giving the date of the original report. Each re-occurrence, complication, or progression of the original event should be reported as a follow-up to that event regardless of when it occurs. The

follow-up information should describe whether the event has resolved or continues, if and how it was treated, whether the blind was broken or not (if applicable), and whether the patient continued or withdrew from study participation.

If the SAE is not previously documented in the Pazopanib Investigator Brochure or Package Insert (new occurrence) and is thought to be related to the Novartis study drug, a DS&E associate may urgently require further information from the investigator for Health Authority reporting. Novartis may need to issue an Investigator Notification (IN), to inform all investigators involved in any study with the same drug that this SAE has been reported. Suspected Unexpected Serious Adverse Reactions (SUSARs) will be collected and reported to the competent authorities and relevant ethics committees in accordance with Directive 2001/20/EC or as per national regulatory requirements in participating countries.

To ensure patient safety, each pregnancy occurring while the patient is on study treatment must be reported to Novartis within 24 hours of learning of its occurrence.

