5.2 Administration

After registration on the protocol, patients will be randomized to receive either pazopanib or temsirolimus treatment. Following randomization patients will begin treatment with the first assigned agent. At progression, if they have not suffered an adverse event that would preclude them from continuing with systemic therapy, after the applicable washout period, will begin treatment with the remaining treatment agent at the discretion of the physician.

Pazopanib will be taken at 800 mg PO daily without food (at least 1 hour before or 2 hours after a meal) until PD or prohibitive toxicity or withdrawal of consent. Tablets will not be crushed due to the potential for increased rate of absorption which may affect systemic exposure. If a dose is missed, it should not be taken if it is less than 12 hours until the next dose. Patients will complete a pill diary for pazopanib to document compliance.

Temsirolimus will be given at 25 mg IV infused over 30-60 minutes every week until PD or prohibitive toxicity or withdrawal of consent. Patients will receive prophylactic intravenous diphenhydramine 25 to 50 mg (or similar antihistamine) approximately 30 minutes before the start of each dose of temsirolimus.

A cycle consists of 4 weeks of therapy. Pazopanib will be self-administered at home and in the outpatient setting for patients who receive temsirolimus.

All patients will have a washout period of 2 weeks from the day of progressive disease tumor assessment before they start 2nd-line therapy.

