Where HR is the hazard ratio (experimental:control). For sample size calculation purposes we assume that the median PFS in the temsirolimus arm is 60% that of the pazopanib arm (3.8 months versus 6.1 months). The sample size estimate is based on a one-sided log-rank test with type one error equal to 0.10 and power of 0.80.

We will conduct an interim analysis for futility after 42 events have been observed. If the p-value used to assess futility at the interim analysis is greater than 0.4798 we will stop the trial early for futility.

Secondary Objectives

Overall survival: Overall survival is calculated from day of therapy initiation to the date of death. Patients who are lost to follow-up will be censored at date of last contact.

We will use the Kaplan-Meier estimator to estimate the OS for each group of patients (control, experimental), and the log-rank statistic will be used to test for treatment differences. We will also use the Cox proportional hazards regression model to estimate the hazard ratio (experimental:control) for OS with a 95% confidence interval.

We will also assess the response rate and report 95% confidence intervals.

Additional analyses:

Demographics

For each treatment group (control, experimental), summary statistics will be provided for age, weight, baseline disease status and prior treatments.

Toxicities

Toxicities and side effects that will be evaluated include, but are not limited to infections, renal toxicity, hepatic toxicity, and pulmonary toxicity. Methods of assessment will include monitoring blood counts, and performing laboratory tests as indicated by clinical signs and symptoms. Evidence of toxicities or adverse events will be recorded at all clinic visits. All observed toxicities and side effects will be graded (NCI CTC-AE v. 4.0) for all patients and the degree of association of each with pazopanib or temsirolimus assessed. The incidence and severity of toxicities will be compared between the two treatment arms with Fisher's exact test.

Stratification Factors

The Pocock-Simon Minimization Method will be used to randomize patients according to the following stratification factors:

- Prior nephrectomy status (yes or no)
- Prior cytokine/vaccine therapy (yes or no)

The randomization program based on this method will be developed in the Department of Biostatistics and Applied Mathematics, and the program will be available via an intranet web site of MD Anderson Cancer Center.

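### Non-serious Grade 1-2 adverse events are recorded only if rated at least possibly related, yet toxicity is compared between arms with no limit by grade or attribution

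*Combined protocol and SAP*

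**What the plan says.** **Capture rule (section 11).** Despite the table's title, the text makes it binding here: "For this protocol adverse events will be captured according to the Recommended Adverse Event Recording Guideline for Phase II protocols (below"). The table crosses attribution with grade and lists in each cell the trial phases that record the event. The row for unrelated events begins "Unrelated Phase I Phase I Phase I Phase II Phase I Phase II Phase III", and the row for unlikely events begins "Unlikely Phase I Phase I Phase I Phase II". In both rows Phase II first appears at Grade 3. In the possible, probable and definitive rows, Phase II appears at every grade.

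**Who attributes (section 11).** The investigator or a physician designee is responsible for "assigning the attribution for each event for all subjects enrolled on the trial".

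**Analysis (section 13, Toxicities).** "All observed toxicities and side effects will be graded (NCI CTC-AE v. 4.0) for all patients", with the degree of association with either drug also assessed. Then: "The incidence and severity of toxicities will be compared between the two treatment arms with Fisher's exact test". No grade or attribution limit is attached to that test.

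**Evaluability (section 14.1).** This section refers to toxicity related to the targeted therapy, in each treatment stage.

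**Treatment (section 5.2).** "Pazopanib will be taken at 800 mg PO daily without food"; "Temsirolimus will be given at 25 mg IV infused over 30-60 minutes every week". No placebo or masking is described.

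**The concern.** The capture rule and the analysis describe different sets of events. Under section 11 a non-serious Grade 1-2 event reaches the data only if someone who can see which drug was given rates it at least possible. Section 13 reads as though every observed toxicity were available for comparison.

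Two problems follow. First, an any-grade incidence or a severity distribution built from these records combines all-cause Grade 3-5 events with attributed-only Grade 1-2 events, so it has no single meaning. Second, the section 3 background describes different profiles for the two drugs. Pazopanib is linked to diarrhea, hypertension, hair color change and raised ALT/AST; temsirolimus to raised glucose, raised lipids and infection. If the same mild event is rated possible more readily on one drug than on the other, part of the recorded difference is a difference in attribution.

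Safety is a secondary objective, and the low-grade profile is part of how two palliative regimens would be compared. Grade 3-5 comparisons are not affected by this filter.

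**Working it through.** The plan gives no figure to reproduce on this point. The check is a reading of the capture table followed by an illustration of what the filter can do.

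**Step 1: what is captured for a Phase II trial (section 11 table).**

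| Attribution | Grade 1-2 | Grade 3-5 |
|---|---|---|
| Unrelated | not captured | captured |
| Unlikely | not captured | captured |
| Possible, probable, definitive | captured | captured |

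Section 13 would need all six cells to be captured. Section 14.1, if read as defining the compared set, would need only the bottom row. The table delivers neither.

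**Step 2: inputs for the illustration.**
- From section 13: 45 patients per arm; Fisher's exact test; two-sided 0.05, the default level for tests not otherwise specified.
- Assumed, because the documents give no values: true Grade 1-2 incidence π, equal in both arms, at 20%, 30% and 40%; and the probability a that an event is rated at least possible, set at 90% in one arm and lower in the other.

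**Step 3: formula.** Recorded incidence = π × a. For example, π = 30% gives 0.30 × 0.90 = 27% in one arm and 0.30 × 0.60 = 18% in the other. The rejection rate is the sum, over all pairs of counts (x, y) from 0 to 45 for which Fisher's two-sided p is below 0.05, of Bin(x; 45, π·a₁) × Bin(y; 45, π·a₂).

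**Step 4: rejection rate with no true difference.**

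| Attribution by arm | π = 20% | π = 30% | π = 40% |
|---|---|---|---|
| Full capture | 2.6% | 3.0% | 3.0% |
| 90% v 80% | 3.0% | 3.6% | 4.5% |
| 90% v 70% | 4.5% | 6.2% | 9.0% |
| 90% v 60% | 7.4% | 11.5% | 17.5% |
| 90% v 30% | 31% | 51% | 70% |

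With equal attribution of 80% in both arms the rate is 2.5% at π = 20% and 3.1% at π = 40%. Spurious differences therefore require attribution that differs by arm.

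**Step 5: loss of a real difference.** Assume a true incidence of 60% v 30%:

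| Attribution (60% arm v 30% arm) | Recorded incidence | Power |
|---|---|---|
| 100% v 100% | 60% v 30% | 75.8% |
| 80% v 80% | 48% v 24% | 59.7% |
| 60% v 60% | 36% v 18% | 39.6% |
| 60% v 90% | 36% v 27% | 10.7% |

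Equal attribution shrinks a real difference without creating a false one; unequal attribution can nearly remove it.

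**The case against.** **The comparison may be meant for treatment-related toxicity.** The section 13 sentence on grading goes on to assess association with each drug, section 14.1 speaks of related toxicity, and the objective concerns safety associated with the treatments. On that reading attribution is part of the definition. This has force: the intended analysis set is undefined, and all-cause comparison is one reading of it. It does not rescue the plan, because Grade 3-5 events enter at any attribution and section 13 sets no filter to remove the unrelated ones.

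**The exclusion is not absolute.** A reader might infer that no mild event is seen unless it is blamed on the drug. The documents do not support that. Section 11 captures serious adverse events without an attribution condition. Scheduled laboratory values such as ALT, AST and glucose could be regraded. The threshold is only possible. Section 13 also says evidence of adverse events is recorded at clinic visits. The point is therefore limited to non-serious Grade 1-2 events, chiefly those not derivable from laboratory results.

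**Equal incidence with unequal attribution is an awkward pairing.** If a drug causes an event, its true incidence is probably higher in that arm, and the filter mainly exaggerates a real difference. If the event is pure background, there is less reason for attribution to diverge. This stands as a caution about the size of the effect. It does not remove the mixing of two capture rules.

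**Low stakes.** Safety is secondary, no decision rule uses these tests, and section 13 disclaims multiplicity adjustment. This limits the point to a correction worth making; it does not threaten the trial's primary conclusion.

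**Conclusion.** The concern holds in limited form. The capture rule in section 11 and the comparison in section 13 cannot both stand as written, and section 14.1 does not reconcile them. Grade 1-2 and any-grade comparisons mix all-cause and attributed events and can be distorted if attribution differs by arm.

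The size and direction are unknown. With equal true incidence of 20-40%, modest attribution gaps keep the false-positive rate at 3.0-4.5% (90% v 80%) or 4.5-9.0% (90% v 70%), against about 3% under full capture. It reaches 7.4-17.5% at 90% v 60%. A reader might take the 31-70% at 90% v 30% as the expected error rate, but nothing in the documents supports so wide a gap; it marks an extreme. All attribution and incidence values are assumptions.

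A reader might also state as fact that this trial is open label. The protocol uses that term only for the earlier phase 3 study of temsirolimus. Here it is an inference, though a strong one, from a daily oral drug against a weekly infusion with no masking or independent attribution described.

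**What to change.** **Preferred.** In section 13, Toxicities, limit the between-arm Fisher comparison to Grade 3-5 events regardless of attribution. Report Grade 1-2 events by arm as investigator-attributed and descriptive, without a test. Reword sections 11, 13 and 14.1 so that they name the same sets of events. The cost is wording only; the downside is no formal test of low-grade toxicity.

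This removes the recording filter but does not make ascertainment equal. Section 5.4 schedules examinations every 4 weeks on temsirolimus and every 8 weeks on pazopanib. On-treatment lipid panels are listed for temsirolimus only, and thyroid tests for pazopanib only. The report should say so.

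**Alternative.** Amend section 11 so that this protocol records all grades regardless of attribution in both arms. The cost is some extra data entry for up to 90 patients. It must be adopted prospectively, because mild events that were never recorded may not be recoverable.

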12.0 CRITERIA FOR REMOVAL FROM PROTOCOL TREATMENT

Subjects who meet the following criteria should be discontinued from study treatment:

- Progressive disease: Patients, who develop rapidly progressive disease before the scheduled evaluation, may be taken off study at the discretion of the investigator, if they are not felt to be candidates to begin treatment with the second agent.
- Intercurrent illness that, in the opinion of the treating physician/investigator, prevents continuation of treatment.
- Decision of the patient to withdraw from the study, or patient non-compliance with therapy.
- Grade \geq 2 pulmonary or CNS hemorrhage; any Grade 4 hemorrhage
- Any grade arterial thromboembolic event
- Grade 4 congestive heart failure
- Gastrointestinal perforation
- Wound dehiscence requiring surgical intervention

13.0 STATISTICAL CONSIDERATIONS

This is a randomized, two-arm, parallel group, phase II trial enrolling advanced, poor-risk, clear-cell RCC. Patients will be fairly randomized to either temsirolimus (control arm) or pazopanib (experimental arm).

The maximum sample size to be accrued is 90 patients (45 in each treatment arm). The primary measure of efficacy and primary endpoint is progression free survival (PFS). PFS will be monitored on an interim basis and we will use stopping rules for futility to serve as guidelines for early termination. The stopping rules are ad-hoc in nature but are selected in a manner such that the overall type 1 error is controlled at a one-sided 10% with 80% power.

Descriptive and inferential statistics will be used to summarize treatment effects. The mean, standard deviation, median, 25% percentile, 75% percentile, minimum, and maximum will be reported for continuous variables. For discrete variables, descriptive analyses will be based on the distribution of discrete outcomes and will be reported as percentages and patient counts. Time to event endpoints will be descriptively summarized by Kaplan-Meier curves. Point and interval estimates of treatment effect will be based on maximum likelihood methods. For binomially distributed variables, we will report differences in proportions between treatment groups and the 95% confidence interval associated with those differences. We will estimate treatment effects for time to event variables via hazard ratios using Wald scores from Cox proportional hazard regression models. Unless stated otherwise, all statistical tests will be assessed using a two-sided $\alpha = 0.05$ alpha significance level and confidence intervals will be constructed using two-sided 95% and will be based on the normal approximation. Although multiple secondary endpoints will be evaluated we will make no adjustment for multiplicities associated with these multiple tests.

Estimation of Sample Size

The clinical hypothesis we are assessing in this trial is whether patients receiving the experimental therapy have a lower hazard of progression or death relative to patients receiving the control therapy. The statistical hypothesis is stated as:

$$H_0: \log(HR)=0$$

$$H_A: \log(HR)<0$$

Where HR is the hazard ratio (experimental:control). For sample size calculation purposes we assume that the median PFS in the temsirolimus arm is 60% that of the pazopanib arm (3.8 months versus 6.1 months). The sample size estimate is based on a one-sided log-rank test with type one error equal to 0.10 and power of 0.80.

We will conduct an interim analysis for futility after 42 events have been observed. If the p-value used to assess futility at the interim analysis is greater than 0.4798 we will stop the trial early for futility.

Secondary Objectives

Overall survival: Overall survival is calculated from day of therapy initiation to the date of death. Patients who are lost to follow-up will be censored at date of last contact.

We will use the Kaplan-Meier estimator to estimate the OS for each group of patients (control, experimental), and the log-rank statistic will be used to test for treatment differences. We will also use the Cox proportional hazards regression model to estimate the hazard ratio (experimental:control) for OS with a 95% confidence interval.

We will also assess the response rate and report 95% confidence intervals.

Additional analyses:

Demographics

For each treatment group (control, experimental), summary statistics will be provided for age, weight, baseline disease status and prior treatments.

Toxicities

Toxicities and side effects that will be evaluated include, but are not limited to infections, renal toxicity, hepatic toxicity, and pulmonary toxicity. Methods of assessment will include monitoring blood counts, and performing laboratory tests as indicated by clinical signs and symptoms. Evidence of toxicities or adverse events will be recorded at all clinic visits. All observed toxicities and side effects will be graded (NCI CTC-AE v. 4.0) for all patients and the degree of association of each with pazopanib or temsirolimus assessed. The incidence and severity of toxicities will be compared between the two treatment arms with Fisher's exact test.

Stratification Factors

The Pocock-Simon Minimization Method will be used to randomize patients according to the following stratification factors:

- Prior nephrectomy status (yes or no)
- Prior cytokine/vaccine therapy (yes or no)

The randomization program based on this method will be developed in the Department of Biostatistics and Applied Mathematics, and the program will be available via an intranet web site of MD Anderson Cancer Center.

Data Analyses for Quality of Life Measures

Prior to inferential procedures, extensive descriptive analyses will be conducted for each of the measures obtained at each session. Descriptive statistics (e.g., means, ranges, standard deviations) will be computed, together with ninety-five percent confidence intervals for the means. Proportions of subjects falling outside normative ranges for the stress and QOL measures will also be calculated. Values for the standardized scales will be compared to normative data and patients receiving other types of cancer therapy. Graphical methods (e.g., boxplots and histograms) will be employed to more closely examine the distributions of the

measures at each time point. Change scores for the stress and QOL measures will be computed as the simple differences between the baseline measure and subsequent evaluations. Bivariate associations between the raw scores, the change scores, optimism, social support, and demographic variables will be evaluated using Pearson's product moment correlation coefficients together with scatterplots where appropriate. These procedures will allow us to thoroughly characterize the stress and QOL profiles of this patient population across the sessions.

In this study, numerous models will be constructed to analyze the data and, therefore, the results will be treated as hypothesis generating and interpreted with caution. Inferential statistics will comprise paired t-tests of the stress and QOL measures. Significant test results ($p < .05$) will be interpreted as indicating significant changes in depression and QOL associated with the treatment. The association between depression and survival and TTP will also be examined.

